- *Note: The following exceptions to laboratory normal reference ranges are allowed: Creatinine, Blood Urea Nitrogen (BUN), total bilirubin, AST, ALT, lipase, amylase, Prothrombin Time (PT), Partial Thromboplastin Time (PTT) below the lower limit of normal (LLN); CK less than 400U/L; Glucose, potassium, total protein, and alkaline phosphatase with a toxicity grade of 1 is allowable; albumin above the upper limit of normal (ULN).*
- *Laboratory values that are outside the range of eligibility but are thought to be due to an acute condition or due to laboratory error may be repeated once.*

11. The urine drug screen is negative

12. Breathalyzer test is negative

13. Available for follow-up for the duration of the study

14. Agrees not to participate in vigorous activity 72 hours prior to dosing through day 15 post dosing

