6.5.2. Safety Laboratory Tests

The following laboratory tests will be done at screening and end of study. Subjects should be fasting. This means no food or drink (other than water) for at least eight hours prior to sampling.

Safety labs with a Grade 1 value (Appendix B) will not exclude a subject from participation but will serve as their baseline value.

- Hematology: hemoglobin, WBC with differential, absolute neutrophil count and platelet count. MCV, MCH, MCHC, RDW, MPV, which are included in a complete blood count with differential, will not be graded.

- Chemistry: serum creatinine, BUN, calcium, total bilirubin, direct bilirubin, indirect bilirubin, alkaline phosphatase, PT, PTT, INR, ALT, AST, sodium, potassium, and total CK.
- Urinalysis: dipstick: Urine protein, blood and glucose must be negative or trace. Menstruating females failing with a positive blood on urine dipstick may be retested following cessation of menses.

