8.5. Halting Rules

8.5.1. Halting Criteria for the Study

Study dosing can be halted at any time if medically indicated. Study dosing must be stopped, and a review of available safety data will be conducted by the SRC if any of the following occur:

1. Death of a dosed subject following injection and prior to the subject's last visit that was not the result of trauma or accident, and possibly related to study product.
2. Occurrence of a life-threatening allergic/hypersensitivity reaction (anaphylaxis) in any subject, manifested by bronchospasm with or without urticaria or angioedema or requiring hemodynamic support with pressor medications or mechanical ventilation.
3. One subject with an SAE.
4. Two or more subjects with a Grade 3 AE in the same organ class (systemic toxicity, clinical laboratory tests or vital signs) regardless of relatedness to study drug. An exception to this includes scenarios where there are obvious and acceptable physiological explanations for a Grade 3 abnormality (e.g., Grade 3 hematuria in a menstruating female).

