10.3.3.2. Additional Safety Analyses

Vital signs, physical examinations, and clinical laboratory values, including change from baseline, will be summarized by dose cohort and control group.

Descriptive summary statistics for laboratory data at admission (baseline value) and each applicable post-injection visit, including change from the baseline value, will be calculated. Descriptive summary statistics for vital signs at screening (baseline value) and each applicable post-injection visit, including change from the baseline value, will be calculated. Shift tables, showing individual subject changes from baseline will be presented for laboratory parameters using toxicity grading (Appendix B). Subjects with Graded values of vital sign and laboratory parameters will be identified in listings.

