Illness or clinical AE (as defined according to applicable regulations)	No interference with activity	Some interference with activity not requiring medical intervention	Prevents daily activity and requires medical intervention

*Will not be used as halting criteria

Laboratory and Vital Signs Reference Ranges, Eligibility Ranges, and Toxicity Grading

Laboratory Adverse Events*	Mild	Moderate	Severe	ICON Normal Lab Values
	(Grade 1)	(Grade 2)	(Grade 3)	
Blood, Serum, or Plasma				
Sodium (hyponatremia) – mEq/L	131-132	129-130	<129	133 – 143
Sodium (hypernatremia) – mEq/L	144 – 145	146 – 147	>147	133 – 143
Potassium (hyperkalemia) – mEq/L	5.2 – 5.4	5.5 – 5.6	>5.6	3.5 - 5.1
Potassium (hypokalemia) – mEq/L	3.2-3.4	3.0 – 3.1	<3.0	3.5 - 5.1
Glucose (hypoglycemia) – mg/dL	65 – 69	55 – 64	<55	70 – 105
Glucose (hyperglycemia) – mg/dL Fasting	106 – 125	126 – 200	>200	70 – 105
Blood Urea Nitrogen – mg/dL	21-26	27 – 31	> 31	6 – 20
Creatinine (Male) – mg/dL	1.3 – 2.0	2.1-2.3	>2.3	0.7-1.2
Creatinine (Female) – mg/dL	1.0 – 1.7	1.8 – 2.0	>2.0	0.5 - 0.9
Calcium (hypocalcemia) – mg/dL	8 - <LLN	7.5 – 7.9	<7.5	8.7 - 10.3
Calcium (hypercalcemia) – mg/dL	ULN - 10.8	10.9 – 11.4	>11.4	8.7 - 10.3
CK-U/L	309-1000	1001-1500	>1500	39-308
Albumin (hypoalbuminemia) – g/dL	2.8 – 3.4	2.5 – 2.7	< 2.5	3.5 - 5.2
AST – U/L (Male)	40-97	98-195	>195	<40
AST – U/L (Female)	32-77	78-155	>155	<32
ALT – U/L (Male)	41-100	101-200	>200	<41
ALT – U/L (Female)	33-80	81-160	>160	<33
Alkaline phosphatase – IU/L (Male)	131-260	261-390	>390	40-130
Alkaline phosphatase – IU/L (Female)	106-210	211-315	>315	35-105
Total Bilirubin (serum) – mg/dL	1.3-1.5	1.6-1.9	>1.9	0 - 1.2
Direct Bilirubin – mg/dL	NA	NA	NA	0.0-0.2
Chloride –mEq/L (hypochloremia)	NA	NA	NA	96-108
Chloride –mEq/L (hyperchloremia)	NA	NA	NA	96-108
CO2 –mEq/L (hypo)	NA	NA	NA	20- 30
CO2 –mEq/L (hyper)	NA	NA	NA	20- 30
Total Protein – g/dL	5.5 - 5.9	5.0 - 5.4	<5.0	6.0 - 8.0
Phosphorus- mg/dl (hypo)	2.3-2.4	2.1-2.2	<2.0	2.5 – 4.5
Phosphorus-mg/dl (hyper)	NA	NA	NA	2.5 – 4.5
Total Cholesterol-mg/dl	NA	NA	NA	<201
Triglycerides-mg/dl	NA	NA	NA	<151
HDL – mg/dl	NA	NA	NA	>65 F >55 M

Laboratory Adverse Events*	Mild	Moderate	Severe	ICON Normal Lab Values
	(Grade 1)	(Grade 2)	(Grade 3)	
LDL Direct – mg/dL	NA	NA	NA	<130
Hemoglobin (Male) – g/dL	11.2 - 12.2	10.0 – 11.1	<10.0	12.3-17.3
Hemoglobin (Female) – g/dL	9.8 - 10.8	8.5 - 9.7	<8.5	10.9 - 14.6
WBC Increase – cell/mm ³	10,001– 15,000	15,001 – 20,000	> 20,000	4,000-10,000

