## 7.22.2 Clinical Laboratory Assessments

Safety Population will be used to present summaries and listings. Clinical laboratory data will be listed and summarized using System International (SI) units.

Laboratory data will be listed by subject at each time point. Clinical laboratory values that are out of normal ranges will be presented in a separate listing.

Observed and change from baseline of continuous clinical laboratory values (serum chemistry, coagulation panel, hematology, and urinalysis) for each parameter will be summarized by dose cohort and control group at each scheduled nominal time point. Categorical Urinalysis will be presented in the listing.

The number and percentage of subjects with shift from baseline based on the laboratory normal ranges will be tabulated.

For female subjects, urine/ serum pregnancy test results will be presented in the individual subject data listings for each visit.

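### The SAP tabulates laboratory shifts by normal range where the protocol requires Appendix B toxicity grade, so the shift table cannot show worsening by grade

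*SAP*

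**What the plan says.** **Protocol.** Section 10.3.3.2 states: "Shift tables, showing individual subject changes from baseline will be presented for laboratory parameters using toxicity grading (Appendix B"). It adds: "Subjects with Graded values of vital sign and laboratory parameters will be identified in listings". Section 3.2.1 makes changes from baseline in clinical safety laboratory values part of the primary endpoints.

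**SAP.** Section 7.22.2 states: "The number and percentage of subjects with shift from baseline based on the laboratory normal ranges will be tabulated". Its listing follows the same rule: "Clinical laboratory values that are out of normal ranges will be presented in a separate listing". Section 8 contains one laboratory shift table, Table 14.3.5.2, and no laboratory table or listing title there mentions grade. Sections 1 and 4 state agreement with protocol version 3.0, and the revision history records no change on this point.

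**Baselines that are already graded.** Protocol 6.5.2 allows them: "Safety labs with a Grade 1 value (Appendix B) will not exclude a subject from participation but will serve as their baseline value". Among the exceptions in inclusion criterion 10 (protocol 4.1.1) are: "CK less than 400U/L; Glucose, potassium, total protein, and alkaline phosphatase with a toxicity grade of 1 is allowable".

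**Grades and ranges.** Appendix B, under "Laboratory and Vital Signs Reference Ranges, Eligibility Ranges, and Toxicity Grading", prints the three grades and the normal range for each parameter in one table, so the two classifications can be compared row by row.

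**The concern.** A normal-range classification has three levels: low, normal and high. Appendix B has four levels in each graded direction: ungraded, Grade 1, Grade 2 and Grade 3. Moving the shift table from the second scale to the first loses two things.

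- Shifts of different size are pooled. A subject who goes from normal to Grade 1 is counted with one who goes from normal to Grade 3.
- Worsening from a graded baseline disappears. A subject who starts at Grade 1 and moves to Grade 2 or 3 generally stays in the same out-of-range category and counts as no shift.

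The table the protocol asked for would show how many subjects at each dose, and on pooled placebo, worsened to Grade 2 or 3. The planned table cannot. Because the SAP claims consistency with the protocol, a reader of the study report would not be told that the scale had changed.

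**Working it through.** The plan gives no figure to reproduce here. The check compares the two scales.

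**1. Row-by-row mapping.** Inputs: every Appendix B laboratory row with Grades 1 to 3, split by direction, sex or race where the table does so (48 rows), and the normal range printed in the same row. Each grade interval was assigned to low, normal or high.

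| Result | Rows |
|---|---|
| Grades 1, 2 and 3 share an out-of-range category | 48 of 48 |
| All three grades lie wholly in that category | 47 of 48 |
| Part of Grade 1 lies inside the normal range | 1 of 48 |

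A typical row is male ALT. Normal is below 41 U/L, Grade 1 is 41-100, Grade 2 is 101-200 and Grade 3 is above 200. All three grades are high.

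**2. Rows where the scales cross.** The one exception is WBC increase in African American males. Grade 1 is 9,001-14,000 but the printed normal range is 4,000-10,000, so 9,001-10,000 is Grade 1 and also normal. Five other race-specific rows go the opposite way, with values that are ungraded but out of range:

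- WBC increase, African American females: 10,001-11,000
- WBC decrease, African American males and females: 2,500-3,999
- Neutrophil decrease, African American males and females: 1,300-1,699

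So the normal-range table can hide shifts that exist on the protocol's scale, and can also show shifts that do not.

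**3. A graded baseline that worsens.** CK: normal 39-308 U/L, Grade 1 309-1000, Grade 3 above 1500. Criterion 10 admits CK below 400, so 309-399 is eligible and already Grade 1.

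- 1501 / 399 = 3.8
- 1501 / 309 = 4.9

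A rise of 3.8- to 4.9-fold, from Grade 1 to Grade 3, is high at both times and is tabulated as no shift.

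**4. Urine.** Appendix B grades urine protein, glucose and microscopic blood. SAP 7.22.2 sends categorical urinalysis to a listing, but the note limiting content to continuous tests is attached to Table 14.3.5.1, not 14.3.5.2. Whether dipstick results enter the shift table is therefore unclear.

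**The case against.** The strongest reply is that little is lost, because grade can be recovered elsewhere. Protocol 8.1 counts an abnormal laboratory finding as an adverse event. Section 8.2.1 records worsening of a baseline condition as one, and severity follows Appendix B where specified. The CK case above should then appear as a severe event in Table 14.3.1.3. All values are listed, and Table 14.3.5.1 gives minimum and maximum by cohort and visit.

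This stands as a limit on the consequence. A reader might infer that grades cannot be told apart anywhere in the report, and the documents do not support that. The other outputs are still not a substitute:

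- The severity table covers only findings recorded as adverse events, and shows no movement from baseline grade.
- Minimum and maximum do not count subjects, and often cannot be graded because limits differ by sex. AST of 156-195 U/L is Grade 3 in women and Grade 2 in men; creatinine of 2.1-2.3 mg/dL likewise.
- The listings leave grading to the reader, in SI units, while Appendix B uses conventional units for creatinine, BUN, calcium, bilirubin and hemoglobin.

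Three other stronger readings also fail.

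- *That the halting rules are weakened.* The study rule is "Two or more subjects with a Grade 3 AE in the same organ class (systemic toxicity, clinical laboratory tests or vital signs"), and protocol 8.5.2 likewise acts on adverse-event grades. For escalation, the Safety Review Committee reviews uncoded data to Day 8 (8.5.3). None of this uses Table 14.3.5.2.
- *That every planned result is affected.* The safety panel has 21 graded blood analytes, and there are 4 post-dose draws in 40 subjects: 21 x 4 x 40 = 3,360. That is the number of planned results at full completion. A value that is normal and ungraded at baseline and stays so reads the same on either scale.
- *That Grade 1 baselines are expected throughout.* They are permitted. Within this panel, criterion 10 allows Grade 1 chemistry at screening only for CK, potassium and alkaline phosphatase. Criterion 8 excludes low hematology values, and urine protein and glucose must be negative or trace.

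**Conclusion.** The point holds as an undeclared conflict between the current protocol and SAP. The planned shift table pools Grades 1 to 3 in each direction, can show no shift when a Grade 1 baseline worsens, and departs from the protocol's scale in both directions in the race-specific rows. The abnormal-value listing has the same mismatch with the protocol's requirement to identify graded values.

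The size is minor. It concerns the summary of one primary safety endpoint, not data collection, subject protection or dose escalation. The number of results shown differently depends on how many graded values occur, which cannot be known beforehand. The conclusion assumes that the normal ranges used for Table 14.3.5.2 are those printed in Appendix B. Race-specific ranges at the laboratory would change the crossing rows in step 2 but not the pooling of grades.

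**What to change.** Add to SAP 7.22.2:

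> For each laboratory parameter graded in Appendix B, counts and percentages of subjects moving from each baseline grade (0, 1, 2, 3) to each grade at every scheduled post-dose visit, and to the worst post-baseline grade, will be tabulated by dose cohort and pooled placebo. Low and high scales will be separate where both exist. Grades will be assigned in Appendix B units before conversion to SI units, using the sex- and race-specific limits. For urine protein and glucose, negative or trace is Grade 0. Urine blood is graded by microscopy when done.

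Keep the normal-range shift table beside it. Appendix B grades neutrophils, platelets, hemoglobin and lymphocytes for decreases only, so replacing the table would drop high shifts; protocol 2.3.1 reports a neutrophil increase as a related event with the similar product NTM-1631. Direct and indirect bilirubin, MCV, MCH, MCHC, RDW and MPV have no grade and also need the normal-range table.

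Flag grades in Listings 16.2.8.2 and 16.2.8.3. If the sponsor prefers normal-range shifts alone, SAP Section 4 should declare and justify the departure.

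Cost: one added or extended table and a grade column in two existing listings. No new data.

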### **7.22.3 Vital Signs**

Vital signs data will be listed by subject at each nominal time point. Observed and change from baseline vital signs values will be summarized by dose cohort and control group at each nominal timepoint.

### **7.22.4 Electrocardiograms**

ECG data will only be listed.

### **7.22.5 Physical Examinations**

Physical examination findings will be listed individually for each nominal timepoint. Shift from baseline and table describing finding as normal/abnormal will be presented for each nominal timepoint.

### **7.22.6 Prior and Concomitant Medications**

All prior and concomitant medications will be listed. A separate listing will be provided for concomitant procedures.

### **7.22.7 Other Observations Related to Safety**

Hypersensitivity panel data if available will be listed. Reactogenicity data will be listed and summarized as described in Section [7.22.1](#).

## **7.23 Planned Interim Analysis**

A blinded interim safety and PK analysis is planned for this study to analyze all PK, ADA, and MNA samples for Cohorts 1-3 through Day 60 and Day 120. This will include all subjects in all cohorts through Day 60 and Day 120. A second blinded interim safety analysis is planned to analyze all PK, ADA, and MNA samples for Cohort 4 through Day 90. Stopping criteria are for safety and are defined in Section 9.5 of the protocol.

The ICON PK scientist will be unblinded to the treatment assignment for that particular cohort to facilitate a more detailed assessment of the PK and ADA data, which may include individual patient demographic and safety data. The ICON PK scientist will provide a summary of the PK and ADA analysis, including individual patient data, but will not include the unique patient number to ensure the Investigators and Sponsor remain blinded or any other individual data that may unblind.

## 7.24 Statistical Software

PK parameters will be calculated using Phoenix™ WinNonlin®, version 8.0 or later. All data listings, summaries, and statistical analyses will be generated using SAS GRID Linux/SAS Studio.

## 7.25 General Conventions for Tables, Listings and Figures

Tables and listings will be presented in landscape mode with minimum of 3/4" bound edge margin and 3/8" other margins on 8.5" x 11" paper.

Times new roman font size of no less than 8 point will be used for tables and listings.

A source line will be included on the bottom of each page of all tables and listings. It will contain the SAS code program name and the run date and time.

Each variable is recorded to a specific number of decimal places. If the raw data is presented with varying precision, then the least precise value will be considered as the data precision.

For summary tables, unless otherwise specified, the number of decimal places provided in the tables and listings will be based on the accuracy of the least accurate value in the raw data as follows:

n	integer
Arithmetic mean	1 decimal place more than the least accurate number in the raw data
SD	2 decimal place more than the least accurate number in the raw data
CV(%)	2 decimal places
Geometric mean	1 decimal place more than the least accurate number in the raw data
Geometric CV	2 decimal places
Median	1 decimal place more than the least accurate number in the raw data
Minimum	same number of decimal places as raw data
Maximum	same number of decimal places as raw data
Percentage	1 decimal place

## 8. LIST OF TABLES, FIGURES, AND LISTINGS

Table/Figure Number	Table/Figure Name
Section 14.1	Demographic and Subject Characteristics Data Summaries
Table 14.1.1	Summary of Subject Enrollment and Disposition (All Subjects)
Table 14.1.2	Summary of Analysis Populations
Table 14.1.3	Summary of Demographic and Baseline Characteristics (Safety Population)
Section 14.2	Pharmacokinetic and Immunogenicity Data Summaries
Section 14.2.1	Pharmacokinetic Data Summaries
Table 14.2.1.1	Summary of Pharmacokinetic Concentrations (PK Analysis Population) Note: separate for each monoclonal antibody and serotype
Table 14.2.1.2	Summary of Pharmacokinetic Parameters (PK Analysis Population) Note: separate for each monoclonal antibody and serotype
Figure 14.2.1.1	Plot of Mean (SD) Serum Concentration-Time Profile (PK Analysis Population) Note: separate for each monoclonal antibody and serotype
Section 14.2.2	Immunogenicity Data Summaries
Table 14.2.2.1	Summary of Anti-drug Antibody Titers (PK Analysis Population) Note: separate for each monoclonal antibody and serotype
Table 14.2.2.2	Summary of Anti-drug Antibody status (PK Analysis Population) Note: separate for each monoclonal antibody and serotype
Section 14.3	Safety Data Summaries
Section 14.3.1	Displays of Adverse Events
Table 14.3.1.1	Overall Summary of Treatment-Emergent Adverse Events (Safety Population)
Table 14.3.1.2	Summary of Treatment-Emergent Adverse Events by System Organ Class and Preferred Term (Safety Population)
Table 14.3.1.3	Summary of Treatment-Emergent Adverse Events by System Organ Class, Preferred Term, and Maximum Reported Severity Grade (Safety Population)
Table 14.3.1.4	Summary of Treatment-Emergent Adverse Events by System Organ Class, Preferred Term, and Closest Relationship to Study Drug (Safety Population)
Table 14.3.1.5	Overall Summary of Reactogenic Adverse Events (Safety Population)

Table 14.3.1.6      Summary of Reactogenic Adverse Events by System Organ Class, Preferred Term, and Maximum Reported Severity Grade (Safety Population)

Table 14.3.1.7      Summary of Reactogenic Adverse Events by System Organ Class, Preferred Term, and Closest Relationship to Study Drug (Safety Population)

**Section 14.3.2      Listings of Deaths, Other Serious and Certain Significant Adverse Events**

Table 14.3.2.1      Subject Listing of Deaths (Safety Population)

Table 14.3.2.2      Subject Listing of Serious Adverse Events (Safety Population)

Table 14.3.2.3      Subject Listing of Adverse Events Leading to Study Discontinuation (Safety Population)

**Section 14.3.4      Abnormal Laboratory Value Listing**

Table 14.3.4.1      Individual Subjects with Abnormal Clinical Laboratory Values (Safety Population)

Note: Please provide reference to Listing 16.2.8.3

**Section 14.3.5      Additional Safety Data Summaries**

Table 14.3.5.1      Absolute and Change from Baseline of Clinical Laboratory Results by Category and Test (Safety Population)

Note: please include only continuous tests

Table 14.3.5.2      Shift from Baseline in Clinical Laboratory Results (Safety Population)

Table 14.3.5.3      Absolute and Change from Baseline for Vital Signs (Safety Population)

Table 14.3.5.4      Shift from Baseline in Physical Examination (Safety Population)

**Listing Number      Listing Name**

**Section 16.2.1      Discontinued Subjects**

Listing 16.2.1      Subject Disposition (Enrolled Subjects)

**Section 16.2.2      Protocol Deviations**

Listing 16.2.2      Protocol Deviations (Safety Population)

**Section 16.2.3      Subjects Excluded from Analysis**

Listing 16.2.3      Analysis Sets

**Section 16.2.4      Demographic Data**

Listing 16.2.4.1      Demographics and Baseline Characteristics (Safety Population)

Note: Including Screening Height and Weight

Listing 16.2.4.2      Screening Outcome (All Subjects)

Listing 16.2.4.3 Eligibility Criteria Satisfaction (Enrolled Subjects)

Listing 16.2.4.4 Consent Information (Safety Population)

Listing 16.2.4.5 Medical and Surgical History (Safety Population)

Listing 16.2.4.6 Prior and Concomitant Medications (Safety Population)

Listing 16.2.4.7 Concomitant Procedures (Safety Population)

**Section 16.2.5 Compliance and/or Drug Concentration Data**

Listing 16.2.5.1 Study Drug Dosing Record and Compliance (Safety Population)

Listing 16.2.5.2 Individual Serum Concentrations (PK Analysis Population)  
Note: separate for each monoclonal antibody and serotype

Figure 16.2.5.1.1 Overlay of Individual Serum Concentration-Time Profiles (PK Analysis Population)  
Note: separate for each monoclonal antibody and serotype

Figure 16.2.5.1.2 Plots of Individual Serum Concentration-Time Profiles (PK Analysis Population)  
Note: separate for each monoclonal antibody and serotype

